8.2.4.4. Subgroup Analysis

To evaluate the relationship between patient background factors and effectiveness, subgroup analyses of the proportion of patients who developed invasive fungal infections and the proportion of patients with successful prophylaxis of invasive fungal infections will be performed in accordance with Section 8.1.3 for each of the factors specified in Section 5.4. Risk ratio and risk difference will not be calculated for concomitant use of steroids or immunosuppressants other than steroids.

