# 7.2.6. Observation period

The observation period shall start on the day the administration of this product begins and ends on the day the administration is completed; provided that the patients will be followed until the last day of the investigation period as long as possible if the administration period prolongs.

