5.4. Subgroup Analysis

Subgroup analyses of safety and effectiveness will be performed for the following patient background factors and other factors. Levels in parentheses are levels of subgroups, and underlined levels are the reference for calculation of risk ratio and risk difference.

- Sex [male, female]
- Age (1) [<15 years, ≥ 15 years]
- Age (2) [<65 years, ≥65 years)
- Age (children 1) [newborns (<1 month after birth), infants (≥1 month to <1 year), younger children (≥1 to <7 years), children (≥7 to <15 years)]
- Age (children 2) [<2 years, ≥ 2 to <15 years]
- Hospitalized Status [inpatient, outpatient]
- Objective of treatment [primary prophylaxis (patients without history of fungal infection), secondary prophylaxis (patients with history of fungal infection), others]
- Type of transplantation [autograft, allogeneic full transplantation, allogeneic mini-transplantation]
- Source of transplantation [bone marrow, cord blood, peripheral stem cell]
- Occurrence of GVHD (graft versus host disease) [absent, present]
- Indication for transplantation¹ [leukemia, myelodysplastic syndrome, malignant lymphoma, myeloma, others]
- Severity of indication for transplantation [mild, moderate, severe]
- Hepatic dysfunction [absent, present]
- Severity of hepatic dysfunction [mild, moderate, severe]
- Renal dysfunction [absent, present]
- Severity of renal dysfunction [mild, moderate, severe]
- Past medical history [absent, present]
- Concurrent illness [absent, present]
- Congenital severe immunodeficiency² [absent, present]
- White blood cell count before administration [$<3000/\mu$ L, $\geq 3000/\mu$ L]
- Neutrophil count before administration [$<500/\mu$ L, $\geq 500/\mu$ L]
- Concomitant use of broad-spectrum antibiotics [absent, present]
- Use of contraindicated concomitant medications [absent, present]
- Use of concomitant medications requiring precautions for coadministration [absent, present]
- Concomitant use of immunosuppressants (other than steroids) [absent, present]
- Concomitant use of steroids [absent, present]
- Concomitant use of steroids or immunosuppressants other than steroids [absent, present]
- Concomitant use of other antifungal agents [absent, present]
- Prior treatment (antifungal agents administered for prophylaxis of invasive fungal infections)
 [absent, present]
- Long-term treatment [$\leq 180 \text{ days}$, $\geq 180 \text{ days}$]

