- Duration of treatment with Vfend (<30 days, \geq 30 to <60 days, \geq 60 to <90 days, \geq 90 to <120 days, \geq 120 to <150 days, \geq 150 to <180 days, \geq 180 days)

¹: Indication will be classified in reference to the Japanese Society of Hematology Guideline for Hematological Malignancies (http://www.jshem.or.jp/gui-hemali/table.html).

²: Congenital severe immunodeficiency is defined as a complication included in MedDRA HLGT "congenital immune system disorders" and "immunodeficiency syndrome" (primary and secondary).

Patients who may meet contraindications in the package insert of Vfend (hereinafter referred to as contraindicated patients) will be extracted based on separately specified criteria, and subgroup analyses of safety will be performed.

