8.1.3. Analysis of Binary Data

The frequency and proportion will be calculated. If the confidence interval of proportion is calculated, two-sided 95% confidence interval (exact method) will be calculated.

If the proportion is compared between subgroups, risk ratio and its 95% confidence interval, and risk difference and its 95% confidence interval will be calculated. In addition, risk ratio and its 95% confidence interval will be graphically presented (see Appendix 2). If the number of patients in at least one category compared is \leq 5, the number of patients and proportion will be calculated but risk ratio and its 95% confidence interval, and risk difference and its 95% confidence interval will not be calculated.

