8.2.3.4. Subgroup Analysis

The number and proportion of patients who experienced at least one adverse drug reaction will be tabulated for each factor specified in Section 5.4. To evaluate the relationship between patient background factors and the development of adverse drug reactions, the analysis specified in Section 8.1.3 will be performed. Risk ratio and risk difference will not be calculated for concomitant use of steroids or immunosuppressants other than steroids.

The listing of adverse drug reactions will be prepared for contraindicated patients. The number and proportion of patients with adverse drug reactions will be tabulated by SOC and PT as necessary.

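### The subgroup risk ratios include treatment duration, which sets the time at risk and is changed by the outcome, so the ratio can differ from 1 with no duration effect

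*SAP*

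**What the plan says.** SAP 5.4 lists the subgroup factors for safety and effectiveness and states that "underlined levels are the reference for calculation of risk ratio and risk difference". Two of the factors are lengths of treatment: long-term treatment, split at 180 days, and a banded factor beginning "Duration of treatment with Vfend (<30 days" and ending at ≥180 days.

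SAP 8.1.3 defines the comparison: crude risk ratio and risk difference with 95% confidence intervals, and "risk ratio and its 95% confidence interval will be graphically presented". Both are dropped if a compared category has 5 or fewer patients.

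For effectiveness, SAP 8.2.4.4 opens "To evaluate the relationship between patient background factors and effectiveness" and says the analyses "will be performed in accordance with Section 8.1.3 for each of the factors specified in Section 5.4". For any ADR, SAP 8.2.3.4 tabulates counts for each 5.4 factor and adds: "To evaluate the relationship between patient background factors and the development of adverse drug reactions, the analysis specified in Section 8.1.3 will be performed". Both sections exempt one factor only: "Risk ratio and risk difference will not be calculated for concomitant use of steroids or immunosuppressants other than steroids". A risk ratio of ≥2 or ≤0.5 leads to a further tabulation (8.2.3.5) or listing (8.2.4.5).

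Protocol 7.2.6 defines follow-up: "The observation period shall start on the day the administration of this product begins and ends on the day the administration is completed". SAP 8.2.3 adds 28 days for safety. Protocol 7.3.5 lists IFI onset and adverse events as reasons for discontinuation. Among the reasons for completion it lists the end of treatment use after a switch from prophylaxis.

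**The concern.** A subgroup ratio is interpretable when the factor is fixed before the outcome and both groups are followed alike. Duration of treatment meets neither condition.

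- It is fixed only by the last dose (SAP 8.2.2).
- It is itself the observation window, so patients treated for ≥180 days have more time in which to have an event. The extra 28 days for ADRs do not equalise this.
- The outcome alters it. An event that stops the drug moves the patient towards the short group. A switch to treatment use moves an IFI case towards the long group.

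Long-term use and factors affecting safety and effectiveness are named objectives (Protocol 6, SAP 2.2). A ratio with a confidence interval, plotted with the other factors, can be read as higher or lower risk with long use when neither exists. The interval does not reveal this bias.

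**Working it through.** **The plan's own figures.** The documents give no figure for this ratio, no distribution of treatment duration and no daily hazard. The only stopping data are discontinuations among patients with hepatic reactions (Protocol 7.5.2, SAP 2.1): 1/47, 2/11 and 2/4, that is 2%, 18% and 50%. Pooled: (1 + 2 + 2)/(47 + 11 + 4) = 5/62 = 8%. These cover only part of all ADRs.

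**Mechanism, checkable by hand.** Assume half of patients are planned for 60 days and half for 240, with a constant IFI hazard giving 10% by Day 180: λ = −ln(0.90)/180 = 0.000585 per day. Duration has no effect on the hazard.

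- Onset does not change duration. Long group: 1 − exp(−240λ) = 13.1%. Short group: 1 − exp(−60λ) = 3.45%. Ratio 13.1/3.45 = 3.8.
- Every onset stops the drug. The long group is the 240-day patients still event-free at Day 180; their risk over the last 60 days is 3.45%. The short group gains the 10% of 240-day patients who had an early IFI: (0.0345 + 0.10)/(1 + 0.10) = 12.2%. Ratio 3.45/12.2 = 0.28.

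This mix exaggerates the contrast. It shows the two opposing mechanisms and is not an estimate.

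**ADR ratio with smoother durations.** Assumed planned duration P: exponential with median 60 or 90 days, or uniform on 30–240 days. The share with P ≥180 days is then 2^(−3) = 12.5%, 2^(−2) = 25% or 60/210 = 29%, before any stopping. Onset is at T. Actual duration D = T if the ADR occurs on treatment and stops it, otherwise D = P. An event is counted if T ≤ D + 28. Ratio = risk with D ≥180 over risk with D <180. Duration has no effect in any scenario. Ratios by share of ADRs that stop treatment:

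| Assumed onset pattern | 0% | 30% | 60% | 100% |
|---|---|---|---|---|
| Constant hazard, 0.002–0.004/day | 1.5–2.8 | 1.2–2.2 | 0.85–1.7 | 0.35–1.0 |
| Gamma frailty, mean 0.004/day, variance 1–2 | 1.4–2.1 | 1.05–1.8 | 0.71–1.35 | 0.22–0.67 |
| Early onset, 40% susceptible, mean 21–45 days | 1.0–1.3 | 0.75–0.97 | 0.47–0.63 | 0–0.03 |

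At the pooled 8%, the ratio is 1.3–2.6 under constant hazard or frailty and 0.94–1.2 with early onset. A ratio of 0.5 or less first appears at about 60% stopping, and then only with early onset.

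**IFI ratio, same durations.** Constant hazard, Day-180 risk 10–20%:

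- every case stops at onset: about 1.0 (exponential) or 0.18–0.19 (uniform);
- half stay on drug 42 more days: 1.3–1.4 or 0.37–0.39;
- half stay on drug 84 more days: 1.7–2.0 or 0.71–0.73.

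If IFI comes early (10–20% susceptible, mean 45 days), the ratio is 0.01–0.18. The success ratio stays at about 0.9–1.3 throughout and does not reach the ≥2 or ≤0.5 screen. In simulated studies of 200 patients, randomly assigned duration labels cross the IFI screen in 8–54% of studies, because cases are few.

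**The case against.** **The analyses are exploratory.** SAP 4.1 treats P values as descriptive and 4.2 has no decision rule. Crossing the screen produces only a listing or a table, and 8.2.3.1 already produces the ADR table by long-term treatment. This stands and makes the point minor.

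**Sounder displays are planned.** Kaplan-Meier covers IFI (8.2.4.3) and the two major investigation items (8.2.3.1). First ADR onset is tabulated in 30-day intervals (8.2.3.1). SAP 8.2.3.5 splits first ADR onset at Day 180 among patients treated for ≥180 days. A reader might infer that the plan leaves long-term safety resting on the crude ratio; the documents do not support that. These displays do not remove the ratio, however, and no Kaplan-Meier analysis of any ADR is planned.

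**The safety wording may not reach duration.** The sentence in 8.2.3.4 names background factors, 5.4 distinguishes these from other factors, and 8.2.2 files treatment period under treatment status. But 8.2.4.4 uses the same phrase to introduce every 5.4 factor, so inclusion is the natural reading, not a certain one. For the seven bands, ratios are only probable, because the underlining that marks reference levels is lost in the text available.

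**The plot already mixes factors.** SAP 5.4 also lists concomitant medication, which is recorded during treatment. That is correct, so the plot should not be described as otherwise purely baseline.

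**Proportions by duration remain and can be divided by hand.** This is true, so the footnote matters as much as the exemption.

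**Conclusion.** The point holds as a minor one. Following SAP 8.2.4.4 as written gives a risk ratio, risk difference and plot for the 180-day split, and these can lie well away from 1 with no duration effect. The same very probably applies to any ADR under 8.2.3.4.

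For ADRs the bias is mainly upward: about 0.94 to 2.6 at 8% stopping. A reader might infer that the ADR ratio could as easily be halved. That needs about 60% or more of ADRs to stop treatment, above every stopping figure in the documents; the highest, 50%, rests on four patients.

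For IFI under constant hazard the ratio runs from about 0.2 to 2.0, depending on the duration distribution and on whether cases stay on drug. A reader might infer that this bias spoils the IFI screen. The counts are too low for that screen to be reliable in any case.

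All sizes rest on assumed durations and hazards, and on carrying hepatic stopping data over to all ADRs. Ratios take <180 days as reference; reversing it gives reciprocals.

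**What to change.** - In SAP 8.2.3.4 and 8.2.4.4, extend the existing exemption sentence to long-term treatment and duration of treatment with Vfend: no risk ratio, risk difference or plot, and no entry to the ≥2 or ≤0.5 screen in 8.2.3.5 and 8.2.4.5.
- Keep the counts and proportions by duration. Add a footnote that they are descriptive and not adjusted for time at risk or for stopping caused by the outcome.
- For long-term use, refer readers to the Day-180 onset split in 8.2.3.5 and to the Kaplan-Meier analyses.

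Person-time rates are not needed. The cost is one phrase in two sentences, a footnote and a cross-reference, with no new data or programming of new analyses. The downside is that no ratio is reported for duration.

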8.2.4.5. Exploratory Analysis

The following exploratory analysis will be performed for factors affecting effectiveness.

 Listings by presence/absence of onset of invasive fungal infections and presence/absence of successful prophylaxis of invasive fungal infections will be prepared by factor with a risk ratio of ≥2 or ≤0.5.

An additional analysis may be performed as necessary. The exploratory analysis will be reported only when results giving important interpretation are obtained.

9. LISTINGS

The following listings will be prepared. Listings with [Intext] specified after the table name are in a format which allows attachment to the report.

Listing of patients⁴

⁴: Estimated creatinine clearance and eGFR before administration will be added to the patient listing. Refer to Appendix 10.3 for calculation method.

- Listing of patients with adverse events
- Listing of patients with adverse drug reactions
- Listing of patients with adverse drug reactions among pediatric patients
- Listing of patients with adverse drug reactions among elderly patients
- Listing of patients with adverse drug reactions among patients with hepatic dysfunction
- Listing of patients with adverse drug reactions among patients with renal dysfunction
- Listing of patients with adverse drug reactions among patients excluded from the safety analysis set
- Listing of patients with serious adverse drug reactions [Intext]
- Listing of deaths [Intext]
- List of events corresponding to safety specifications
- List of adverse drug reactions falling under safety specifications [Intext]
- Listing of laboratory values
- Listing of patients evaluated for effectiveness
- Listing of the status of treatment of Vfend and plasma voriconazole concentration
- List of contraindicated patients
- Listing of prior treatment (antifungal agents administered for prophylaxis of invasive fungal infections)
- Listing of other reasons for discontinuation [Intext]
- Listing of concomitant medications by patient [Intext]

Furthermore, tables corresponding to appendix tables for periodic safety report (PSUR) and application for reexamination will be prepared in accordance with the notification.

10. APPENDICES

10.1. Appendix 1: Details of Data Extraction

A1.1 Definition of Visit Timing

Visit timing	Endpoint	Definition [acceptable range]
Before initiation of treatment	Laboratory test	From 30 days before the day of initial dose in this study (day of initiation of treatment)] to the day of initiation of treatment. If there are multiple days, the date closer to the day of initial dose will be adopted.
At completion of treatment	Laboratory test	On or after the day of last dose in this study. If there are multiple days, the date closer to the day of last dose will be adopted.

10.2. Appendix 2: Examples of Risk Ratio of Incidence of Adverse Drug Reactions by Subgroups

Event name: XXX increased	Category 1		Category 2.		Risk ratio (RR)=	
ø	Number of patients/N-	(%)~	Number of patients/Ne	(%)~	RR-	95 %CI~
Gender (male vs. female)-	18/2220.0	-(0.8)	3/1099.	(0.3)	2.97.	(0.88- 10.06)-
≥65 years vs. <65 years	19/2788-	(0.7)-	2/531-	(0.4)-	1.81-	(0.42=7.74)
Diagnosis (Disease A vs. Disease B)-	3/221-	(1.4)-	18/3 098-	(0.6)-	2.34-	(0.69-7.87)-
Duration of illness (<1 year vs.≥1 year).	9/771-	(1.2)-	7/8:66-	(0.8)	1.44-	(0.54 -3.86)-
Drug A Concomitant use (present ws. absent)-	9/798-	(1.1)-	12/2.521	(0.5)-	2.370	(1.00-5.60)
Drug A Prior treatment (present vs. absent).	1/148	(0.7)-	20/3171-	(0.6)	1.07-	(0.14-7.93)-
Disease B Complications (present vs. absent).	16/1614-	(1.0)-	5/1703-	(0.3)	3.38-	(1.24-9.20)-
Disease B Past medical history (present vs. absent).	7/674	·-(1.0)	14/2:643.	(0.5)	1.96-	(0.79-4.84).
Hepatic dysfunction (present vs. absent)-	0/80-		18/2:056-	(0.9)-	÷	4 ²
Renal dysfunction (present vs. absent)-	1/140	(0.7)-	17/2:004->	(0.8)-	0.84-	(0.11-6.28)

Incidence of Adverse Drug Reaction

10.3. Appendix 3: Formulas to Calculate Estimated Creatinine Clearance and eGFR

Cockcroft-Gault Ccr calculation formula

 $\begin{aligned} \text{Male: Ccr} &= \{(140 \text{ - age}) \times \text{weight (kg)}\} / \{72 \times \text{serum creatinine (mg/dL)}\} \\ \text{Female: Ccr} &= 0.85 \times \{(140 \text{ - age}) \times \text{weight (kg)}\} / \{72 \times \text{serum creatinine (mg/dL)}\} \end{aligned}$

• eGFR calculation formula

Male: eGFR (mL/min/1.73 m²) = $194 \times \text{serum Cr} (\text{mg/dL}) - 1.094 \times \text{age} - 0.287$ Female: eGFR (mL/min/1.73 m²) = $0.739 \times \{194 \times \text{serum Cr} (\text{mg/dL}) - 1.094 \times \text{age} - 0.287\}$

Reference: Evidence-based Clinical Practice Guideline for CKD 2018 - Japanese Society of Nephrology

https://cdn.jsn.or.jp/data/CKD2018.pdf

• Quintic equation

See Page 22 of Guidance for Evaluation of Renal Function at Diagnosis of Pediatric Chronic Kidney Disease (Pediatric CKD)

1. Quintic equation (≥ 2 to <19 years)

With height presented as Ht (m), the reference value of serum Cr will be calculated, and eGFR will be calculated based on the reference value.

	Reference value of serum Cr	
(ED(x), 1, 2, 2, 1, 1, 2, 2) = 110.2	(mg/dL)	1 2 0 2
$eGFR(mL/min/1./3m^2) = 110.2 \text{ x}$ —	Observed value of serum Cr	- + 2.93
	(mg/dL)	
<reference (mg="" cr="" dl)="" of="" serum="" value=""></reference>		

Male:-1.259 Ht⁵ + 7.815 Ht⁴ - 18.57 Ht³ + 21.39 Ht² - 11.71 Ht + 2.628 Female: -4.536 Ht⁵ + 27.16 Ht⁴ - 63.47 Ht³ + 72.43 Ht² - 40.06 Ht + 8.778

Uemura O, et al.Clin Exp Nephrol 2013 : Epub ahead of print

Guidance for Evaluation of Renal Function at Diagnosis of Pediatric Chronic Kidney Disease (Pediatric CKD)

[Edition] 2013 Health Labour Sciences Research Grant for Refractory Disease Research Project (Refractory Disease Research Project)

Group to Elucidate the Natural History of Pediatric Chronic Kidney Disease Including Congenital Anomalies of the Kidney and Urinary Tract and Establish Treatment Methods for Early Diagnosis and Inhibition of

Progression of Renal Failure (Japanese Pediatric CKD Research Group)

[Cooperation] Japan Pediatric Society, Japanese Society of Pediatric Urology, The Japanese Society for Pediatric Nephrology

https://cdn.jsn.or.jp/academicinfo/report/201402.pdf

PPD
